### **4.8 Protection of Clinical Study Patients**

Informed consent will be obtained from each patient prior to initiation of any study activity.

---

Designation of a research proxy will be provided by the research patient; the research proxy will be involved in the patient's study participation if the investigator (or qualified designee) determines at some point the patient is no longer able to make decisions independently.

## **5 INVESTIGATIONAL MEDICINAL PRODUCT**

### **5.1 Assignment of Treatment**

All patients will receive pridopidine (TV-7820, formerly ACR16) 45 mg bid – two active 45 mg capsules taken as two separate doses (90 mg pridopidine per day).

### **5.2 Products**

All products supplied in connection with this study must be used only for this and no other purpose.

All IMP must be stored in a cool dry place below 25°C. IMP must not be frozen or refrigerated.

It is the responsibility of the investigator (or qualified designee) via the mobile nurse to retrieve all unused and all returned used supplies from the patient and to return the supplies to the distributor.

#### **5.2.1 Study Drug**

Company Name: Pridopidine (TV-7820, formerly ACR16)  
Chemical name: 4-[3-(Methylsulfonyl)phenyl]-1-propylpiperidine hydrochloride  
Presentation: White hard gelatin capsules or light pink/white imprinted capsules providing 45 mg pridopidine

#### **5.2.2 Placebo**

Not applicable.

#### **5.2.3 Control Medication**

Not applicable.

### **5.3 Dosage and Administration**

The dose in this study is 45 mg bid. The IMP should be swallowed whole with water. Sufficient IMP will be provided to allow 100% compliance between visits.

The IMP will be dispensed in-person at the VTV and in DTP shipments at 3-month intervals thereafter. Patients may be offered to take the first dose at the investigational center.

#### **5.3.1 Dose Frequency Reduction**

In the event of tolerability problems, patients will be instructed to immediately contact their investigator (or qualified designee) to discuss their AEs. The investigator (or qualified designee) will assess whether or not the AEs could be related to IMP and severe enough to warrant a dose frequency reduction. The patients will be instructed to stop taking 1 of the 2 capsules of their daily dose. Arrangements for an USV at the earliest opportunity will be made (see Section 4.6.5). At this visit patients will be provided with instructions regarding the de-escalated dose frequency. Alternatively, patients may be temporarily off drug up to 60 days per year in the event of tolerability problems, as judged by the investigator (or qualified designee).

---

IMP re-introduction or dose frequency increase back to the previous dose frequency may be considered if the clinical monitor, investigator (or qualified designee), and the patient agree that this should be attempted. Alternatively, qd dosing may be maintained.

Patients should be advised that if tolerability problems continue then they should contact their investigator (or qualified designee) who may then withdraw them from IMP (see Section 7.7.2 for withdrawal procedures).

IMP must be reduced to 45 mg qd for the following events:

- Any QTcF increase >60 ms from the first remote visit
- QTcF  $\geq$ 480 ms and  $\leq$ 500 ms
- Creatinine clearance <60 mL/min and >40 mL/min

If an IMP must be reduced to 45 mg qd and the patient is not currently at a study visit arrangements for an USV at the earliest opportunity will be made (see Section 4.6.5). At this visit, patients will be provided with instructions regarding the de-escalated dose frequency.

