### **6.2 ECG Assessments**

A single resting 12-lead ECG will be performed at VTV and all remote visits by mobile nurses. ECGs will be collected using ECG devices and measures of the cardiac intervals and morphological assessment. Participants have to be resting, in a comfortable supine position and environment, at least 15 minutes before each ECG sampling time point through at least 10 minutes after the collection.

A prolonged QTc interval at the VTV (defined as a QTcF interval of >450 ms for both males and females), or other clinically significant heart conditions as judged by the investigator (or qualified designee) is a violation of exclusion criteria and the patient will not be eligible for participation in the study.

QTcF Formula to be used:  $QTcF = QT/\sqrt{RR}$

Any clinically significant abnormalities observed by the investigator (or qualified designee) must be reported as AEs.

**In instances where there is an increase in QT/QTcF of >500ms or 60ms over the VTV, a second ECG should be repeated after 10 minutes rest to confirm the finding.** Where confirmed, this should be reported and documented on the eCRF as an AE.

Patients with a QTcF interval of >500 ms or if an increase in the average QTcF value is >60 ms from the VTV should be discontinued from the IMP and may remain in the study off IMP. A follow-up ECG should be done in 4 weeks.

If the central ECG reading results match the above criterion, the patient should stop taking IMP and may remain in the study off IMP.

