#### **6.3.2 Laboratory Results Outside the Normal Range**

All laboratory values that fall outside the reference range and are of potential clinical relevance should be noted and commented upon by the investigator (or qualified designee). The appearance of abnormal laboratory results or significant shifts from VTV, considered to be clinically significant by the investigator (or qualified designee) are to be documented as an AE (see Section 7.1.1). Any abnormal laboratory results obtained should be considered by the investigator (or qualified designee) as related to previous use of pridopidine in Open-HART, in which case they will be considered treatment-emergent AEs.

Calcium, magnesium, and potassium levels will be drawn every 6 months [hypokalemia is defined as a potassium level of <3.5 mEq/L]. If <3.5 mEq/L, patient's study drug will be suspended until normal ( $\geq 3.5$  mEq/L).

If hypokalemia is observed, dosing will be interrupted and should not be started again until normal electrolyte values are confirmed by re-draw and maintained for 7 days. Patients needing more than 14 days to reach stable potassium levels, without IMP, should be withdrawn from IMP. The patient will be asked to continue in the study and follow the visit schedule as outlined in the protocol.

[REDACTED], and to ensure a reasonable minimum clearance in all patients through the renal pathway, patients with a creatinine clearance <60 mL/min (calculated by the Cockcroft-Gault formula) will be excluded from the study or may be able to take a lower dosage of IMP (45 mg qd) if his/her creatinine clearance is <60 mL/min and >40 mL/min, per discretion of the investigator (or qualified designee). Patients that de-escalate to half-doses of IMP will have creatinine clearance monitored more frequently than patients at the full dose, as determined by the investigator (or qualified designee). Patients will be discontinued from treatment with IMP if their creatinine clearance decreases to <40 mL/min during their participation in the study. The test may be repeated once, if clinically appropriate.

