### **7.7.1 Cessation of Treatment**

A patient will be classified as having ceased treatment when he or she discontinues IMP, prior to the completion of the prescribed course for any of the following reasons:

- AE
- Death
- Lost to follow up
- Patient withdrew consent
- Major protocol violation
- Pregnancy

- 
- Treatment is no longer appropriate
  - Termination of study

If hypokalemia is observed, dosing will be interrupted and should not be started again until normal electrolyte values are confirmed by re-draw and maintained for 7 days. Patients needing more than 14 days to reach stable potassium levels, without IMP, should be withdrawn from the IMP. The patient will be asked to continue in the study and follow the visit schedule as outlined in the protocol.

In instances where there is an increase in QT/QTcF of >500ms or 60ms over VTV, a second ECG should be repeated after 10 minutes rest to confirm the finding. Where confirmed, this should be reported and documented on the eCRF as an AE.

Patients with a QTcF interval of >500 ms, or with an increase in the average QTcF value >60 ms from the VTV, should be discontinued from the study. A follow-up ECG should be done in 4 weeks.

Patients should also be discontinued if:

- they experience a seizure or convulsions (regardless of the relationship to treatment);
- their body weight decreases to <50 kg (may be discontinued based on investigator (or qualified designee) or Sponsor discretion);
- and/or if creatinine clearance decreases to <60 mL/min (calculated using the Cockcroft-Gault equation). It is allowed to repeat the test once, if clinically appropriate.
- they experience an AE/SAE of suicide ideation or attempt; or
- they have a C-SSRS suicidal ideation score  $\geq 3$  (i.e. who answer "Yes" to questions 3, 4, and 5 in the scale suicidal ideation section); or
- they have a C-SSRS report of suicidal act; or
- they have an abbreviated PBA-s suicidal ideation item score  $\geq 3$  (i.e. 3, 4).

Patients who discontinue treatment with IMP due to safety or tolerability reasons may continue in the study off IMP and perform the scheduled visits and assessments.

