### **7.7.2 Withdrawal**

Patients have the right to discontinue IMP at any time and for any reason. The investigator (or qualified designee) also has the right to discontinue IMP if he/she feels that treatment is no longer appropriate, if in his/her opinion the patient's clinical condition is worsening or for an AE(s).

A complete evaluation, as detailed in the study protocol for the EOS Visit, should be carried out at the time of discontinuation. The patient will then be withdrawn from the study.

If the reason for premature discontinuation is an AE or an abnormal laboratory test result, the principal specific event or test must be reported on the appropriate section(s) of the eCRF.

All patients for whom an AE of suicidal behavior/ideation was reported at any time during the study should be discontinued from IMP and the need for an evaluation by a psychiatrist should be assessed. Discontinued patients should attend an ET visit remotely to return IMP, perform IMP accountability, and will be asked to complete all protocol required study procedures. AEs of suicidal behavior/ideation should be followed until resolution of the suicidal behavior/ideation.

All patients who are discontinued from the IMP due to active suicidal behavior/ideation should be referred to a psychiatrist and followed by the investigator (or qualified designee) until resolution of the suicidal behavior/ideation.

Patients who discontinue IMP due to safety or tolerability reasons may continue in the study off drug and perform the scheduled visits and assessments.

A patient will be considered to have withdrawn from a study in the following circumstances: death, lost to follow-up, if the patient has withdrawn informed consent, or the investigator (or qualified designee) feels that the treatment is no longer appropriate. If withdrawal is due to an SAE the procedure detailed in Section 7.5.3 should be followed.

Patients with a QTcF interval of >500 ms or if an increase in the average QTcF value is >60 ms from the VTV should be discontinued from the study. A follow-up ECG should be done in 4 weeks.

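### The Amendment 05 text gives conflicting dosing orders for creatinine clearance between 40 and 60 mL/min, and inconsistent actions and reference visits for a QTcF rise above 60 ms

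*Protocol*

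**What the plan says.** The protocol supplied is Amendment 05. The full dose is 45 mg twice daily (90 mg/day).

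On creatinine clearance:

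- Protocol 5.3.1: "IMP must be reduced to 45 mg qd for the following events", one of which is "Creatinine clearance <60 mL/min and >40 mL/min".
- Protocol 6.3.2: a patient below 60 is to be excluded, or "may be able to take a lower dosage of IMP (45 mg qd) if his/her creatinine clearance is <60 mL/min and >40 mL/min", with the choice left to the investigator. Drug is stopped if clearance drops under 40 on study.
- Protocol 5.7.7: patients with clearance under 40 are not to receive pridopidine.
- Protocol 7.7.1: a fall in clearance below 60 is listed among the reasons a patient should be discontinued. Section 4.6.9 sends the reader to 7.7.1 for the criteria for stopping IMP in individual patients.
- Protocol 4.5: patients below 60 at the VTV are excluded.
- Protocol 1.3, footnote 15: clearance is checked more often in patients who go down to half dose.

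On QTcF:

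- Protocol 5.3.1: the same mandatory reduction applies to "Any QTcF increase >60 ms from the first remote visit" (RV1), and separately to a QTcF of 480 to 500 ms.
- Protocol 6.2: "increase in the average QTcF value is >60 ms from the VTV should be discontinued from the IMP". The patient may stay in the study untreated.
- Protocol 7.7.1: "increase in the average QTcF value >60 ms from the VTV, should be discontinued from the study". Protocol 7.7.2: "increase in the average QTcF value is >60 ms from the VTV should be discontinued from the study". Yet 7.7.1 also says that those who stop for safety or tolerability "may continue in the study off IMP and perform the scheduled visits and assessments", and 7.7.2 has a similar sentence.
- Protocol 6.2 and 7.7.1: a rise of 60 ms over the VTV is to be confirmed by a second ECG after 10 minutes' rest.
- Protocol 1.3, footnote 12: a QTcF of 480 to 500 ms, glossed in brackets as a rise of at least 60 ms from the VTV, is a safety signal. The response is ECGs every 3 months instead of every 6.

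SAP 2.1 states that the SAP rests on Amendment 04 and that Amendment 05 was issued but not implemented.

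**The concern.** These are dosing rules for renal and cardiac safety, and Protocol 2.3 reports dose-dependent and exposure-dependent QTc findings. An investigator who reads 5.3.1 halves the daily dose. One who reads 7.7.1 or, for QTcF, 6.2 stops it. For QTcF the rules also start from two different ECGs, because RV1 can fall up to 30 days after the VTV. A third difference is whether the patient stays in follow-up off drug or leaves the study.

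The protocol does not say which section takes precedence. The one pointer from 7.7 to 5.3.1 concerns tolerability problems, and nothing extends it to a laboratory or ECG threshold.

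**Working it through.** There is no planned figure to reproduce: Protocol 8.4 and SAP 2.5 state that no sample size calculation was done. The check sets the rules side by side and runs values through them.

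**Creatinine clearance (mL/min)**

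| Value | 5.3.1 reduce to qd (>40 and <60) | 6.3.2 stop (<40) | 7.7.1 discontinue (<60) |
|---|---|---|---|
| 60 | no | no | no |
| 59.9 | yes | no | yes |
| 50 | yes | no | yes |
| 40.1 | yes | no | yes |
| 40 | no | no | yes |
| 39.9 | no | yes | yes |

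Every value strictly between 40 and 60 receives both a reduce and a discontinue instruction. Because 4.5 excludes patients below 60 at the VTV, the usual way into this band is a fall on study, which is the event 7.7.1 acts on.

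The gap can be put in serum creatinine terms. With the Cockcroft-Gault equation in 4.5, clearance = k / serum creatinine, where k = (140 − age) × kg × [0.85 if female] / 72. The serum creatinine at clearance 40 divided by that at clearance 60 is (k/40)/(k/60) = 60/40 = 1.5 for every patient. The patients below are assumed, not trial data.

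| Assumed patient | k | Limit at 60, k/60 (7.7.1), mg/dL | Limit at 40, k/40 (6.3.2), mg/dL |
|---|---|---|---|
| Woman, 60 y, 50 kg | 47.22 | 0.79 | 1.18 |
| Man, 60 y, 60 kg | 66.67 | 1.11 | 1.67 |
| Woman, 45 y, 65 kg | 72.90 | 1.22 | 1.82 |
| Man, 45 y, 80 kg | 105.56 | 1.76 | 2.64 |

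**QTcF rise**

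Assume a later QTcF of 465 ms that is confirmed on repeat and is also the average. It lies below the 480 ms rule, so only the rise matters. Reference values are illustrative.

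| VTV | RV1 | Rise from VTV | Rise from RV1 | 5.3.1 reduce | 6.2 stop |
|---|---|---|---|---|---|
| 400 | 400 | 65 | 65 | yes | yes |
| 400 | 410 | 65 | 55 | no | yes |
| 410 | 400 | 55 | 65 | yes | no |

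In the first row two incompatible orders apply at once. In the other two, a 10 ms difference between the reference ECGs decides which order applies. Wherever 6.2 stops drug, 7.7.1 and 7.7.2 say the patient leaves the study, although both sections also let safety discontinuers continue untreated. Footnote 12 adds another response, more frequent ECGs, to a signal described partly by a 60 ms rise from the VTV.

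**The case against.** The strongest objection is that this text was not in force. The VTV and RV1 belong to the virtual schedule, and the visit schedule in SAP 2.1 contains neither. This stands, and it limits the point. A reader might infer that treated patients received contradictory dosing instructions. The documents do not support that, because the Amendment 04 wording of these sections is not supplied.

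On creatinine, 6.3.2 read in full names two outcomes for a patient below 60 (exclusion, or once-daily dosing between 40 and 60) and says the investigator decides. So it would be too strong to say that the protocol never acknowledges a choice in this band. But exclusion may refer to entry only, and discretion in 6.3.2 does not reconcile a mandatory reduction in 5.3.1 with a discontinuation criterion in 7.7.1. The objection also notes that 5.3.1, 5.7.7, 6.3.2 and footnote 15 all fit reduction between 40 and 60 and stopping below 40, so the intent can be recovered. That is right, and it is why the correction is straightforward.

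On QTcF, 5.3.1 speaks of any increase, while the stop rules speak of the average value and follow a confirmatory repeat ECG. A staged rule is therefore a plausible reading: reduce on any rise, stop on a confirmed one. The single ECG per visit does not rule it out, since the repeat supplies a second reading. But the protocol does not state it, a confirmed rise still meets both rules, and staging would not explain the two reference visits.

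A reader might also infer that stopping must override reducing. The documents do not settle this. Section 5.3.1 uses the stronger verb, footnote 12 is compatible with monitored continuation, and part of the dose and safety rationale is redacted.

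**Conclusion.** The point holds as an internal inconsistency in the safety dosing rules of the issued Amendment 05 text. The creatinine conflict is the clearer one. It covers the whole open interval from 40 to 60 mL/min, and the limit of 60 in 7.7.1 is the outlier. The QTcF conflict is also real: a rise above 60 ms has different actions in 5.3.1, 6.2 and 7.7.1/7.7.2, counted from two reference visits, with footnote 12 adding a further response. Which action is right is a clinical decision.

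The size lies in the action: 45 mg or 0 mg a day for the same patient. The factor of 1.5 in serum creatinine only restates 60/40, and some change of action near a cut-off is normal for any threshold rule. The QTcF and patient values above are assumed, and the documents give no frequency for such events.

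A reader might infer that the trial's results are affected. That is not shown. The SAP analyses are descriptive, the SAP contains no rule on when a QTcF or creatinine value changes the dose, and no planned summary is shown to change. Whether anyone was managed under similar wording depends on Amendment 04. The inconsistency is still worth correcting, because it concerns safety thresholds and the repair is a matter of wording.

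**What to change.** 1. In 7.7.1, change the creatinine clearance limit from below 60 to below 40 mL/min, in line with 5.3.1, 5.7.7, 6.3.2 and footnote 15. A value of exactly 40 would then fall under no rule, so make the lower bound in 5.3.1 inclusive.
2. In 5.3.1, measure the QTcF rise from the VTV, so that all the QTcF rise rules share one reference.
3. In 7.7.1 and 7.7.2, have the QTcF rule withdraw the patient from IMP rather than from the study, with continued follow-up off drug allowed, as 6.2 already does.
4. Have the sponsor state one action for a confirmed rise above 60 ms and, if staging is intended, say what an unconfirmed rise triggers. Stopping, as in 6.2, is the conservative option. If it is chosen, delete the bullet on the 60 ms rise from 5.3.1. Make footnote 12 consistent with the choice.
5. Check the version sites follow (Amendment 04, according to SAP 2.1) for the same wording, and correct it there if present.

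The cost is a wording amendment or clarification letter, with no new procedures or patients. If the sponsor chooses stopping, some patients with a rise above 60 ms will come off drug who could have continued at the reduced dose.

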### 5.3.2 Investigational Medicinal Product

Capsules will be swallowed whole with water. One capsule should be taken early in the morning and one in the afternoon 7 to 10 hours after the morning dose, irrespective of food.

### 5.3.3 Placebo/Control Medication

Not applicable.

## 5.4 Presentation and Packaging

Teva will provide the IMP. The primary packaging of the 30- and 60-count bottles will be done at [REDACTED] and the secondary packaging and labeling of the IMP will be contracted to [REDACTED].

An interactive response technology (IRT) system will be used to manage the inventory and distribution of IMP to patients, track IMP, and manage the returns and destruction of the product at the conclusion of the study. At the VTV, patients will receive a 6-month supply of IMP. After the VTV, 3-month supplies of IMP will be distributed directly to the patient via DTP shipments.

The IMP will be packed in high-density polyethylene bottles of 30 or 60 capsules per bottle. Four 30-count bottles will be packaged in a patient specific box (for 60-count bottles, kits will contain 4 bottles). Kits will be provided for each patient according to the dosing schedule at the VTV and at 3-month intervals thereafter. Each box for DTP shipping is good for approximately 3 months of dosing. Patient will take home 4 kits at the VTV, and subsequent kits will be shipped directly to the patient. Patients will be provided with an information sheet. This will include instructions for the patient, in case of tolerability problems, to contact the investigator (or qualified designee) immediately. Separate dosing instructions will be provided for those patients de-escalating their dose frequency.

The label texts will be completed in accordance with the appropriate country regulatory requirements.

## 5.5 Blinding

Not applicable. This is an open-label study with no blinding.

## **5.6 Accountability of Investigational Medicinal Product and Patient Compliance**

A record will be kept by the IRT system of all IMP shipped to the patient, used, and returned. This record gives details of what IMP each patient received.

All unused IMP and used packaging will be returned by the mobile nurse to the distributor at each visit, and stored until notice of destruction from the Sponsor.

Any re-labeling will be in accordance with the appropriate Good Manufacturing Practices/Good Clinical Practice (GCP) requirements.

The electronic Case Report Form (eCRF) will be used by the mobile nurse to perform IMP accountability during remote visits. Patient compliance will be assessed via inquiry during TCs and by capsule count when the mobile nurse visits the patient. The mobile nurse should count the number of capsules remaining in the treatment packs and discuss with the patient any discrepancies between numbers of capsules taken and numbers which should have been taken since the last visit, and record patient compliance in the eCRF.

## **5.7 Concomitant Medication**

### **5.7.1 CYP2D6 Substrates With a Narrow Therapeutic Margin**

[REDACTED] in this study, medication containing CYP2D6 substrates with a narrow safety margin, e.g. class I anti-arrhythmics and tricyclic antidepressants, must not be used.

To be eligible for inclusion, patients must not have taken any such drug within 6 weeks of the first remote visit. Patients who are prescribed such medication during the study treatment period must be withdrawn from the study (see Section 7.7.2).

